## 2 Abbreviations

ADR	Adverse Drug Reaction
AE	Adverse Event
ANOVA	Analysis of Variance
ASIS	Anterior Superior Iliac Spine
BMI	Body Mass Index
CD36	Cluster of Differentiation 36
CRP	C-reactive protein
FDA	Food and Drug Administration
GAIS	Global Aesthetic Improvement Scale
GCP	Good Clinical Practice
HIV	Human Immunodeficiency Virus
ICF	Informed Consent Form
IQR	Interquartile Range
IRCT	Iranian Registry of Clinical Trials
MedDRA	Medical Dictionary for Regulatory Activities
MRI	Magnetic Resonance Imaging
PT	Preferred Term
SAE	Serious Adverse Event
SD	Standard Deviation

### **3 General Information (Administrative Information)**

#### **3.1 Scientific Title of the Study**

Evaluating the efficacy and safety of Embella (Deoxycholic acid, produced by Espad Pharmed Darou Company) for the treatment of flank fat

#### **3.2 Study Registration**

- Ethics Code:
  - Name of University of Medical Sciences/Name of Institution: Tehran University of Medical Sciences  
Code: IR.TUMS.MEDICINE.REC.1402.700  
Date: 04/03/2024
- Study Registration Code in the Iranian Registry of Clinical Trials (IRCT):  
IRCT20240416061507N1

#### **3.3 Date and Revision Number of the Protocol**

Protocol Revision Number: 1.1

Date: 23/08/2025

**Roles and Responsibilities:**

- Conducting the study in accordance with the protocol approved by the Ethics Committee
- Establishment of a Team for Conducting the Study
- Holding training sessions for new and current team members whenever necessary
- Approval and supervision of the appropriate site for product storage
- Approval and Supervision of an Appropriate Site for Candidate Admission
- Non-disclosure of the information contained in the protocol and study data without written permission from Espad Pharmed Darou Company (except to the extent necessary for obtaining informed consent from individuals for whom the product will be prescribed).

#### Roles and Responsibilities:

- Conducting the study in accordance with the protocol approved by the principal investigator and ethics committees.
- Establishment of a Team for Conducting the Study at the Participants Recruitment Site
- Non-disclosure of the information contained in the protocol and study data without written permission from Espad Pharmed Darou Company and the principal investigator of the study (except to the extent necessary for obtaining informed consent from individuals for whom the product will be prescribed).
- Holding training and practice sessions for new and current team members whenever necessary
- Preparation of an Appropriate Site for Participants Admission
- Preparation of an appropriate location for the storage of products used in the study

### 3.5 Introduction

With the increasing demand for body contouring, non-invasive or minimally invasive methods for reducing localized fat in various areas of the body have gained growing popularity over the past decade (1). Localized adipose deposits are typically found in regions such as the abdomen, flanks, thighs, inner knee, arms, and others. Although diet, exercise, and bariatric surgery may be effective in controlling obesity, aesthetic procedures remain necessary for the removal or reduction of localized fat deposits in areas resistant to these interventions, such as the flanks and abdomen. Liposuction is the most common method for reducing excess localized fat; however, as an invasive surgical technique, it is associated with complications such as pain, infection, prolonged recovery, scarring, hematoma, deep vein thrombosis, pulmonary embolism, and anesthesia-related adverse effects. These complications, along with the extended recovery period, have led patients to seek alternative, less invasive methods for body contouring. Currently, non-invasive fat reduction techniques include low-level lasers, radiofrequency, ultrasound, infrared light, cryolipolysis, and the use of injectable solutions containing fat-dissolving agents. Treatments that are minimally invasive and not accompanied by the aforementioned complications are ideal for patients seeking reduction of localized fat for body contouring (2).

Multiple clinical trial studies have been reported in the field of adipose tissue reduction through subcutaneous injection of solutions containing phosphatidylcholine and bile salts, specifically sodium deoxycholate, and consequently, these treatments have gained significant popularity. Studies have demonstrated that deoxycholate is the primary active ingredient in the aforementioned injectable solutions and is responsible for the clinical reduction of adipose tissue (3).

Synthetic purified deoxycholic acid has been introduced as the first pharmacological intervention approved by the FDA for the reduction of submental fat. Deoxycholic acid is a type of bile acid which, due to its ability to induce non-selective cell lysis and disruption of adipocyte membranes (adipocytolysis), leads to the emulsification of fat in the intestine (4,5). Deoxycholic acid has been used for the reduction of localized fat for three decades. Its mechanism of action involves the emulsification of phospholipids and subsequent dissolution of biological membranes, which leads to adipocyte necrosis. In a prospective study conducted in 2017, the efficacy and safety of a 1.25% sodium deoxycholate solution were evaluated in 221 patients with various forms and degrees of localized fat. Injections were administered into the adipose tissue at 6-week intervals and continued until clinical results were achieved.

Outcomes were assessed using before-and-after photographs and patient satisfaction was measured by completion of an anonymous form, while adverse events (AEs) were reported by the treating physician. Among 185 patients eligible for final evaluation, the mean treatment efficacy score reported by patients was 7.4, and medical assessment indicated treatment success in 93.5% of cases. AEs were mainly mild and localized at the injection site, with the incidence of severe complications being very rare. The results of this study confirm the efficacy and safety of deoxycholic acid injections for the reduction of localized fat (6).

In another study, the efficacy and safety of deoxycholic acid injection in the abdominal area were evaluated in 7 female patients. The results indicate that its mechanism of action is through the increase of crown-like structures and macrophage infiltration, as well as the reduction of leptin expression, hormone-sensitive lipase, triglyceride lipase, and CD36, ultimately resulting in adipose tissue necrosis. In the evaluation of systemic inflammatory markers, including CRP, lipid profile, and blood glucose, no significant changes were observed (7).

Given that non-invasive methods have subtle effects that are not immediately observable, various objective and subjective techniques are utilized to assess their efficacy. In most studies, measurement of the circumference of the target area before and after the intervention is reported as an indicator. Other objective techniques, such as the use of calipers, ultrasound, MRI, and three-dimensional photography, have also been employed. Common subjective methods include the evaluation of standardized photographs by a blinded assessor and patient satisfaction surveys. All existing methods for quantifying non-invasive fat reduction have significant limitations and cannot be relied upon independently (11).

## **4 Study Objectives and Hypotheses**

### **4.1 Study Hypothesis:**

The injectable solution containing deoxycholic acid (Embella, manufactured by Espad Pharmed Darou Company) demonstrates appropriate efficacy and safety in the reduction of lateral abdominal fat.

### **4.2 Primary Objective:**

The aim of this study is to determine the efficacy and safety of the injectable solution containing deoxycholic acid (Embella, manufactured by Espad Pharmed Darou Company) in reducing fat in the flank area.

### **4.3 Secondary Objectives:**

- The proportion of participants who, at week 6, according to the investigator's assessment on the GAIS score, have achieved a score of 1 or higher (improved, much improved, or very much improved).
- Changes from baseline in waist circumference at weeks 6 and 12 using a flexible measuring tape.
- Changes from baseline in body weight at weeks 6 and 12.
- Changes from baseline in right and left thigh circumference at weeks 6 and 12 using a flexible measuring tape.
- Changes from baseline in flank fat on each side measured by caliper at weeks 6 and 12.

- Assessment of the trend in dermal and hypodermal thickness changes on both sides by measurement with ultrasonography from baseline to weeks 6 and 12
- Assessment of participants' satisfaction at weeks 6 and 12
- Assessment of the incidence of AEs following treatment

## 5 Study Design and Methodology

### 5.1 Study Population:

- **Inclusion Criteria:**

1. Men and women aged between 21 and 65 years
2. Presence of mild to moderate flank fat, as assessed by the investigator and ultrasound and/or caliper (with a thickness of  $\geq 2$  cm of adipose tissue at the posterior axillary lines at the level of the ASIS).
3. Signing of the informed consent form by the participants
4. Ability to comply with study instructions and likelihood of completing all required visits
5. Agreement to abstain from any treatment in the flank area, including botulinum toxin, hyaluronic acid fillers, cosmetic surgery, laser/light therapy, chemical peels, etc., throughout the study period.

- **Exclusion Criteria:**

1. Planning for lifestyle modification during the predicted duration of the study
2. History of liposuction or laser lipolysis surgery within the past 12 months, or intention to undergo these procedures
3. Significant weight loss in the past 6 months or planned weight loss during the anticipated duration of the study
4. Body mass index (BMI) greater than  $30 \text{ kg/m}^2$
5. Waist circumference greater than 105 centimeters
6. Affliction with uncontrolled systemic diseases
7. Severe cardiovascular diseases

8. Known hypersensitivity or allergy to the study product or its components
9. Pregnant women, breastfeeding women, or women who are expected to become pregnant during the anticipated duration of the study
10. Current enrollment in a drug or investigational device study, or participation in such a study within the past 30 days, as well as during the course of the study.
11. Previous treatment of the flank area with hyaluronic acid fillers or semi-permanent fillers within the past 12 months
12. Use of permanent fillers or silicone in the flank area
13. Individuals who intend to undergo cosmetic procedures in the treatment area during the study, or who have a history of cosmetic procedures (such as surgery) or visible scars in that area that may affect the assessment.
14. Individuals with volume loss due to trauma, adipose tissue disorders associated with autoimmune diseases such as generalized lipodystrophy (e.g., in juvenile dermatomyositis), localized lipodystrophy (such as Barraquer-Simons syndrome), hereditary diseases, or HIV-associated disease
15. Infection or skin diseases at the injection site
16. Evidence of recent alcohol or drug abuse
17. Medical and/or psychiatric conditions of such severity that they may interfere with the outcomes of the study
18. Having a known bleeding disorder or the use of medications that increase the likelihood of bleeding after injection
19. Presence of hair in the flank area that interferes with assessment or treatment
20. Predisposition to hypertrophic scar formation
21. History of anaphylaxis or allergy to lidocaine (or other amide anesthetics), hyaluronic acid products, or streptococcal proteins
22. Affliction with Porphyria
23. Presence of active inflammation, infection, malignant or premalignant lesion, or non-healed ulcer in the flank region

24. Having a condition or being in a situation which, in the opinion of the investigator, may place the individual at significant risk, disrupt the study results, or interfere with the individual's participation in the study.

- **Withdrawal Criteria:**

1. Withdrawal of participant from informed consent
2. Non-compliance, including refusal to adhere to the medical requirements of the study, failure to undergo procedures specified in the study protocol, or use of prohibited medications.
3. Inability to follow up on the participant's status
4. Treatment of the flank area with hyaluronic acid fillers or semi-permanent fillers during the course of the study
5. The use of any permanent filler or silicone materials in the flank area during the course of the study
6. Undergoing any cosmetic procedures in the treatment area during the study period (such as surgery)
7. Having conditions that, in the opinion of the investigator, may interfere with the assessment of efficacy

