## **5.2 Study Outcomes and Methods of Assessment:**

### **Primary Outcome**

- The proportion of participants who, at week 12, according to the investigator's assessment on the GAIS score, have achieved a score of 1 or higher (improved, much improved, or very much improved).

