### **Secondary Outcome(s)**

- The proportion of participants who, at week 6 based on the investigator's assessment on the GAIS score, have achieved a score of 1 or higher (improved, much improved, or very much improved).
- Changes from baseline in waist circumference at weeks 6 and 12 using a flexible measuring tape.
- Changes from baseline in body weight at weeks 6 and 12.
- Changes from baseline in right and left thigh circumference at weeks 6 and 12 using a flexible measuring tape.
- Changes from baseline in flank fat on each side measured by caliper at weeks 6 and 12.
- Assessment of the trend in dermal and hypodermal thickness changes on both sides by measurement with ultrasonography from baseline to weeks 6 and 12
- Assessment of participant satisfaction at weeks 6 and 12
- Assessment of the incidence of AEs following treatment

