### 5.3 Study Schedule Table

	Study Duration			
	Screening	Intervention	Follow-up	
Time Point	Screening Visit	Visit 1	Visit 2	Visit 3
Time	Day -7 to -1	Day 0	Week 6 ± 1 week	Week 12 ± 1 week
Informed Consent Form	×			
Assessment of Inclusion and Exclusion Criteria	×			
Medical History	×			
Physical Examination and Vital Signs		×	×	
Concomitant Medications	×	×	×	×
Skin Ultrasonography	×		×	×
Photography		×*	×	×
Intervention		×	×**	
GAIS Assessment			×	×
Assessment of Participant Satisfaction				×
Adverse Event Assessment	×	×	×	×

\* Photography must be performed prior to injection.

\*\* In case a touch-up injection is deemed necessary by the physician.

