## **6 Sample Size Calculation Method**

In this study, 30 participants will be enrolled.

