#### **Secondary Endpoint Analysis**

Descriptive analysis of data for quantitative variables will be reported as mean and standard deviation (SD) or median and interquartile range (IQR), based on the data distribution, and for qualitative variables as the number and percentage. Changes over time will be analyzed using repeated measures analysis of variance (repeated measures ANOVA) or the Friedman test, depending on the data distribution. Comparisons between baseline and subsequent timepoints will also be performed using the paired t-test or the Wilcoxon test, as appropriate. The significance level for the tests will be considered as 0.05.

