Study Design	The present study is an interventional, single-arm, open-label study conducted in Iran, to evaluate efficacy and safety of Embella (Deoxycholic acid, produced by Espad Pharmed Co.) for the treatment of flank fat
Sponsor	Espad Pharmed Company
Principal Investigator	Investigator: [name] Affiliation: Tehran University for Medical Sciences, Department of Dermatology, Pemphigus Research Unit, Razi Hospital, Tehran, Iran
Co-investigators	[name] Tehran University of Medical Sciences, Cancer Research Center
Investigational Drug	Embella (Deoxycholic acid, produced by Espad Pharmed Co.)
Sample size	The sample size is not determined based on a statistical power calculation. 30 subjects will be studied.
Eligibility criteria	
Inclusion Criteria:
 
 1. Men and women aging between 21 to 65 years 2. Having mild to moderate flank fat assessed by the investigator and sonography and/or caliper (≥ 2cm thickness of the fat tissue in posterior axillary lines at the level of ASIS) 3. Signing informed consent by the subject 4. Ability to follow study instructions and likely to complete all required visits 5. Agreement to abstain from any treatment to the flank region, including botulinum toxins, hyaluronic acid fillers, cosmetic

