	
17. Medical and/or psychiatric problems that are severe enough to interfere with the study results18. Known bleeding disorder or receiving medication that will likely increase the risk of bleeding after injection19. Having hair that would interfere with evaluation and treatment of the flank area20. Being prone to develop hypertrophic scarring21. Having a history of anaphylaxis or allergy to lidocaine (or any amide-based anesthetics), hyaluronic acid products, or Streptococcal protein22. Having porphyria23. Having an active inflammation, infection, cancerous or precancerous lesion, or unhealed wound in the flank area24. Having a condition or being in a situation that, in the investigator's opinion, may put the subject at significant risk, may confound the study results, or may interfere significantly with the subject's participation in the study
Randomization	The subjects will not be randomly allocated because the study is single arm and all subjects will receive Embella.
Blinding	This study is open-label and there is no blinding in this study
Intervention	Deoxycholic acid, SC, 0.15 ml each injection, up to 2-4 ml in each site (2 ml at visit 1 for everyone, and 2 ml at visit 2 unless the patient does not agree)
Efficacy and Safety outcomes	
Primary endpoint:
 
The proportion of participants with grade 1 or higher (“improved, much improved, very much improved”) in investigator-assessed Global Aesthetic Improvement Scale (GAIS) at Week 12
 
Secondary endpoints:
 
Secondary endpoints:
 
1. Safety assessment by evaluation of adverse events (AEs)2. The proportion of participants with grade 1 or higher (“improved, much improved, very much improved”) in

	
investigator-assessed Global Aesthetic Improvement Scale (GAIS) at Week 6
 
3. Change from Baseline in ultrasonographic measurement of dermal and hypodermal thickness on both flanks at weeks 6 and 124. Changes from Baseline in the bodyweight (Kg) at Weeks 6 and 125. Changes from Baseline in right and left thigh circumference at Weeks 6 and 12 using a flexible tape measure6. Changes from Baseline in caliper measurement (mm) of flank fat on each side at Weeks 6 and 127. Changes from Baseline in waist circumference at Weeks 6 and 12 using a flexible tape measure8. Subject's satisfaction at Weeks 6 and 12 using a 10-point Likert scale

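### The screening ultrasound can both admit a participant at 2 cm or more and serve as the only pre-treatment scan, so regression to the mean can produce an apparent fall in hypodermal thickness

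*Protocol*

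**What the plan says.** **Entry.** Protocol 5.1, criterion 2, requires "Presence of mild to moderate flank fat, as assessed by the investigator and ultrasound and/or caliper". The SAP synopsis gives the floor as at least "2cm thickness of the fat tissue in posterior axillary lines at the level of ASIS", and SAP Section 3 repeats the rule. The instrument is left open. The only upper limit on flank fat is the mild-to-moderate wording, which carries no figure.

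**Timing.** In Protocol 5.3 the row "Skin Ultrasonography" is marked at Screening (Day -7 to -1), week 6 and week 12, and is blank at Visit 1. The SAP Study Timeline is the same. Caliper measurement has no row in either table.

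**Endpoint and test.** A secondary outcome is "Assessment of the trend in dermal and hypodermal thickness changes on both sides by measurement with ultrasonography from baseline to weeks 6 and 12". Protocol 6.1 adds: "Comparisons between baseline and subsequent timepoints will also be performed using the paired t-test or the Wilcoxon test, as appropriate". SAP Section 6 sets a two-sided 0.05 level. Neither document defines the ultrasound baseline, plans a repeat pre-treatment reading, or mentions regression to the mean.

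**Design.** "The subjects will not be randomly allocated because the study is single arm and all subjects will receive Embella". Protocol section 6 states: "In this study, 30 participants will be enrolled".

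**The concern.** When one reading both admits a participant and serves as baseline, the admitted group's baseline is selected partly on measurement error. Someone truly a little under 2 cm enters only if the reading errs high, and someone a little over is turned away if it errs low. On average the admitted readings are too high, and the next reading falls back with no treatment effect.

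A control arm would show the same fall and cancel it. Here there is none, and the within-group tests compare the later scans directly with the selected one. The repeated measures ANOVA and Friedman test use the same baseline and share the problem.

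This matters because the primary endpoint is an unblinded investigator rating, and the Protocol's introduction concedes that no single method of measuring fat reduction is sufficient alone. The ultrasound and caliper results are the natural corroboration, so a built-in drift towards reduction weakens that support.

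**Working it through.** **No plan figure to reproduce.** The SAP synopsis says the 30 participants do not come from a power calculation. Neither document gives a thickness mean, SD or reliability.

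**Inputs from the documents.** Cut-off 20 mm, n = 30, two-sided 0.05 (so 2.5% in the direction of a reduction), paired t-test.

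**Assumed inputs.** Screened-population mean 20, 23 or 26 mm; SD of a single reading 5 or 7 mm; reliability R of a single reading 0.80, 0.90 or 0.95; normal distributions; one reading per participant, at the same site for entry and outcome; no true change.

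**Case 1: ultrasound alone qualifies.** A share 1 − R of the variance of a reading is error, so the expected error in the admitted readings is

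false reduction = SD × (1 − R) × φ(z) / (1 − Φ(z)), with z = (20 − mean)/SD.

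- A. Mean 20, SD 5, R 0.80: z = 0; 5 × 0.20 × 0.3989/0.5000 = 0.80 mm.
- B. Mean 23, SD 7, R 0.90: z = −0.429; 7 × 0.10 × 0.3639/0.6659 = 0.38 mm.
- C. Mean 26, SD 5, R 0.90: z = −1.2; 5 × 0.10 × 0.1942/0.8849 = 0.11 mm.
- Largest in the grid (mean 20, SD 7, R 0.80): 7 × 0.20 × 0.3989/0.5000 = 1.12 mm.
- Smallest (mean 26, SD 5, R 0.95): 5 × 0.05 × 0.1942/0.8849 = 0.05 mm.

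**Cases 2 to 4, by simulation.** Caliper and ultrasound have equal reliability and independent errors; groups of 30; no true change. Each cell gives the mean false reduction and the chance of a significant reduction.

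| Scenario | Ultrasound alone qualifies | Either may qualify | Caliper alone qualifies | Baseline from a separate Visit 1 scan |
|---|---|---|---|---|
| A | 0.80 mm, 28% | 0.33 mm, 8% | 0.0 mm, about 2.5% | 0.0 mm, about 2.5% |
| B | 0.38 mm, 9% to 10% | 0.16 mm, 4% to 5% | 0.0 mm, about 2.5% | 0.0 mm, about 2.5% |
| C | 0.11 mm, 4% to 5% | 0.04 mm, 3% | 0.0 mm, about 2.5% | 0.0 mm, about 2.5% |
| Whole grid | 0.05 to 1.1 mm, about 4% to 28% | about 0.02 to 0.47 mm, 3% to 8% | none | none |

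**Effect of an upper limit.** If mild to moderate worked as a ceiling on the same scan, with w = (ceiling − mean)/SD, the formula becomes

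SD × (1 − R) × [φ(z) − φ(w)] / [Φ(w) − Φ(z)].

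With an assumed ceiling of 30 mm:

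- B: w = 1; 0.7 × (0.3639 − 0.2420)/(0.8413 − 0.3341) = 0.17 mm, with about 5% false significance.
- C: w = 0.8; 0.5 × (0.1942 − 0.2897)/(0.7881 − 0.1151) = −0.07 mm, a false increase, with about 2% false significance for a reduction.

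**Outside the grid.** If most people screened lie below the cut-off, the effect grows. With ultrasound as sole gate, mean 15 mm, SD 8 mm and R 0.80, it is 1.97 mm, with 57% false significance.

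**The case against.** The strongest reply is that the criterion does not make ultrasound the gate. A site could qualify everyone by caliper, and if caliper and ultrasound errors are independent the ultrasound endpoint then shows no regression. This stands. The ultrasound-only figures are an upper case, and the effect is possible rather than certain.

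Second, the same criterion says mild to moderate, and participants with BMI above 30 or waist above 105 cm are excluded. Selection at the top pulls the other way. This also stands, although no ceiling on thickness is stated or tied to the scan, so the net direction cannot be settled from the documents.

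Third, the scope is narrow. Selection is on adipose thickness, so it bears on the hypodermal part of the endpoint and not directly on dermal thickness. The documents do not say that the outcome scan is taken at the eligibility site. In scenario B the admitted mean is 23 + 7 × 0.3639/0.6659 = 26.8 mm, so a bias of 0.38 mm is about 1.4% of it. An uncontrolled study cannot attribute change to the product in any case. All this limits the weight of the point but does not remove it: a known source of drift can be taken out at little cost.

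A reader might go further and infer that both objective measures are biased towards a reduction. The documents do not support that for caliper. With no schedule row its baseline visit is unknown, and the problem arises only if the qualifying caliper reading is reused as baseline.

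**Conclusion.** The point holds as a possibility built into the design. A scan that can admit a participant is the only scheduled ultrasound baseline, and nothing in a single-arm paired comparison would reveal regression to the mean.

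The size rests on the mean, SD and reliability assumed above and on which instrument qualifies. It ranges from nothing under caliper-only entry, through the either-instrument figures, to about 1.1 mm and 28% at the upper end of the grid. It is negligible if most candidates are well above 2 cm, and an effective upper limit could reverse it.

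It would be wrong to infer that the trial's main efficacy result is distorted by this route. The primary outcome is "The proportion of participants who, at week 12, according to the investigator's assessment on the GAIS score, have achieved a score of 1 or higher", which is not a change from the screening scan. This is a worthwhile, inexpensive correction to a secondary endpoint.

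**What to change.** **Change.**
- Move the ultrasonography mark from Screening to Visit 1, before injection, in both schedule tables.
- Qualify on the Screening caliper, and amend criterion 2 to say so in Protocol 5.1, the SAP synopsis and SAP Section 3.
- Add caliper rows to both schedules, with a fresh pre-injection reading at Visit 1 as the caliper baseline.
- State in SAP Section 4 that the qualifying reading is never the baseline for a change endpoint.

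**Cost.** Ultrasound-only qualification is given up, so who qualifies may change slightly. There is one brief extra caliper reading per side, and the apparent mean reduction may be a little smaller. No ultrasound session is added. If the site wants to keep ultrasound for entry, the Screening scan can stay and a Visit 1 scan be added as baseline, at the price of one session. A second probe placement at the same visit would be weaker, because error shared by both readings that day remains.

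**If participants are already enrolled.** Report the ultrasound and caliper changes by qualifying instrument where it was recorded, and state regression to the mean as a limitation.

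The change removes this selection effect only. Other drift over 12 weeks remains inseparable from treatment without a control arm.
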